**Sponsor: The George Washington University Medical Faculty Associates**

**Funding Source: Janssen Scientific Affairs, LLC**

## PROTOCOL SYNOPSIS

Protocol Title:	Role of Canagliflozin on gene expression and function of CD34+ endothelial progenitor cells in patients with type 2 diabetes
Site Numbers & Names	GWU Medical Faculty Associates
Research Hypothesis:	Type 2 diabetes is associated with poor stem cell number and function. Poor viability and function of EPCs in diabetes affects the repair and regeneration of the endothelium. We hypothesize that use of Canagliflozin (Cana), along with certain anti-diabetic drugs may help reduce cardiovascular risk by improving EPC survival and function above and beyond adequate glucose metabolism control.
Study Schema: Drugs / Doses / Length of Treatment	
We propose a 2-arm randomized, parallel group, longitudinal study of 16-week intervention duration. The 16-week time interval has been previously shown adequate to observe changes in biochemistry, EPCs and, importantly, pulse wave velocity (PWV) changes. Patients will be randomized to 2 groups:
 
Control (n=20) Concomitant Anti-Diabetic Therapy + Placebo.  Treatment (n=20) Concomitant Anti-Diabetic Therapy + Cana 100mg.


Study Objectives:
 
 
• Primary
 
• Secondary
 
	
The primary objective is to ascertain if the addition of Cana improves CD34+ cell function and gene expression in type 2 diabetes patients, which will be correlated to improvement in 24hr urinary protein estimation and creatinine clearance (obtained via micro-albumin/creatinine ratio from a spot urine sample).
 
The secondary objective is to correlate the cellular outcome measures with other measures of endothelial function such as:
 
 
1. Arterial stiffness measures with Pulse wave analysis and pulse wave velocity measurements.
 
2. Serum biochemistry looking at surrogates of endothelial health, endothelial inflammation, appetite controlling hormone levels and fasting glucose, insulin and lipid profile.
 
3. Resting Metabolic Rate measurement
 
 
Study Outcome Measures:
 
Primary:
 
To investigate the effect of Cana on Endothelial function in patients inadequately controlled (HbA1C <math>\geq</math> 7.0 % to <math>\leq</math>10%) while being treated with a stable dose of certain anti-diabetic drugs.
 
 
• Cellular markers. We will study pre and post Cana treatment changes in number, function and gene expression of patients' peripheral blood-derived CD34+ cells.
 
• Renal Function Estimation: 24hr urinary protein estimation, creatinine clearance and urine exosome study.
 
 
Secondary:
 
To investigate the effect of Cana treatment on:
 
 
• Serum endothelial inflammatory markers including high sensitivity C-reactive protein (hs-CRP), IL-6, TNF-alpha and fasting lipid profile.
 
• Glycemic control will be evaluated by measuring fasting blood glucose, insulin, and HbA1c levels and assessing insulin resistance using HOMA-IR.
 
• Adiposity, measured using a body composition analyzer scale, measured as percentage body fat.
 
• Creatinine clearance estimation.
 
• Vessel health will be assessed by systolic and diastolic blood pressure and Arterial stiffness assessed using Vascular Flow and wave measurement equipment, SphygmoCor CP system from ATCOR.
 
• Central and aortic blood pressure estimated by the sphygmocor system.
 
• Resting Metabolic Rate (RMR, similar to Resting Energy expenditure measurement) at baseline, midway point (week 8) and post therapy.
 

--	---

Study Design:	Prospective, double-masked, randomized placebo-controlled trial
Accrual Goal (Total number of subjects):	N = 40
Accrual Rate (Number of subjects expected per month):	Recruit 40 patients in approximately 36 months
Estimated Timeline:	FPFV: 10-06-2016 LPLV: 01-06-2019
Co-relative studies (PK/PD, etc.):	N/A
Inclusion Criteria:	
 
1. Adults aged 30-70 years
 
2. Diagnosis of type 2 diabetes using criteria of the American Diabetes Association
 
3. Currently being treated with any combination of the following anti-diabetic therapies: metformin (1-2 grams), insulin, GLP-1 agonists, a DPP-IV inhibitor, or sulfonylureas as therapy for their Type 2 Diabetes
 
4. HbA1C between 7.0 to 10.0 % (both inclusive)
 
5. BMI 25 – 39.9 kg/m^2
 

Exclusion Criteria:	
Patients with:
 
 
1. Type 1 DM
 
2. History of hyperosmolar non-ketotic coma
 
3. Abnormal CBC that is judged by physician to be unsafe to enroll or low hematocrit (<28 UNITS).
 
4. History of Pancreatitis
 
5. History of DKA in the past 3 months
 
6. History of active cancer or cancer treatment in the past 5 years (except basal cell carcinoma)
 
7. Heart attack or stroke within 6 months of screening
 
8. Clinically significant coronary and/or peripheral vascular disease that would be unsafe to enroll in the study.
 
9. Statin use started or dose change in the last 3 months,
 
10. CKD stages 3B-5
 
11. Use of oral anti-diabetic medication other than metformin, insulin, GLP-1 agonists, DPP-IV inhibitors, or sulfonylureas
 
12. Use of consistent long-term steroid medication in the last 3 months (oral, inhaled, injected).
 
13. Uncontrolled inflammatory disease, or current chronic use of anti-inflammatory drugs within the last 3 months.
 
14. Pre-existing liver disease and/or ALT and AST >2.5X's UNL
 
15. Serum creatinine levels ≥2.0
 
16. Estimated CrCl < 45 mL/min (measured by eGFR value)
 
17. Triglycerides >450 mg/dL
 
18. Implanted devices (e.g., pacemakers) that may interact with Body Composition scale
 
19. Untreated Systolic Blood Pressure > 150 mmHg and diastolic Blood Pressure > 90 mmHg
 

	
20. Active wounds or recent surgery within 3 months. 21. Untreated hyper/hypothyroidism
 
Additionally, patients who are active smokers, patients who are pregnant, nursing women, and post-menopausal women who are on estrogen hormone replacement therapy (not including oral contraceptives) will be excluded.
 
Detailed Inclusion / exclusion criteria are listed on pages 12-15 of the protocol.

Criteria for Evaluation: (Efficacy, safety, stopping rules, etc.)
	
Subjects will be phone screened to determine initial eligibility. If the phone-screening indicates possible eligibility, then the subjects will come to an in-person screening visit at week -2, then evaluated for end points at weeks 0, 8 and 16. Follow up phone call will be done 30 days after last dose of study drug to assess for adverse effects.
 
Study participation will be stopped for adverse effects at the discretion of the study investigator. Subjects may stop study participation at any time and for any reason.

Statistics:
	
The total sample size is requested, after accounting for attrition over the 16-week period, is 20 subjects per group or 40 subjects total. Sample size estimates were based on the effects of exercise on CD34+/KDR+ cells as described in the literature. The effect of a single session, as well as extended training, on healthy subjects or those with existing cardiovascular conditions appears to increase the CD34+/KDR+ cells.
 
This is a pilot study; as a result appropriate power calculation is not feasible. We however did conduct power analysis, which provided us with 73% power (see statistics section). A p-value of less than 0.05 will be considered statistically significant.

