### **Effect of Cana on Serum Biochemistry:**

While we believe cell based biomarkers are superior to traditional serum biomarkers, we believe the outcome report will be stronger if one can show positive co-relation between the two outcome measures. We therefore will be looking at:

- I. Inflammation, apoptosis and anti-oxidant protein levels: Highly selective C-reactive protein (hs-CRP), IL-6, TNF-alpha, fasting glucose, insulin and lipid profile.
  - a. Glycemic control will be evaluated by measuring fasting blood glucose, insulin levels and HbA1c. Fasting blood glucose, insulin and lipid profile will be used to assess insulin resistance (32, 37)
- II. Plasma SDF1 alpha (ELISA) and GLP-1 (ELISA) will be estimated to assess endothelial health and factors that may influence CD34+ cell chemotaxis
- III. Estimation of Creatinine Clearance and proteinuria: 24hr urinary protein estimation and creatinine clearance (obtained via micro-albumin/creatinine ratio from a spot urine sample).
  - a. *Subjects will have the option of opting into a sub-study that is being run by [name] at the Veterans Affairs (VA) Maryland Health Care System. 10-20 mL of the excess fresh spot urine that has been collected would be sent to the VA for exosome analysis. This is optional, and is not required of subjects. For details of urine-exosome study please see page 31.*
- IV. The glomerular filtration rate (GFR) will be estimated using the CKD-EPI (Chronic Kidney Disease Epidemiology Collaboration) equation. The CKD-EPI equation, expressed as a single equation, is:
  - a.  $GFR = 141 \times \min(Scr/\kappa, 1)^a \times \max(Scr/\kappa, 1)^{-1.209} \times 0.993^{Age} \times 1.018$  [if female]  $\times 1.159$  [if black]; where Scr is serum creatinine (mg/dL),  $\kappa$  is 0.7 for females and

0.9 for males,  $\alpha$  is  $-0.329$  for females and  $-0.411$  for males, min indicates the minimum of  $Scr/\kappa$  or 1, and max indicates the maximum of  $Scr/\kappa$  or 1.

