## **4 TREATMENTS**

### **STUDY TREATMENT: CANAGLIFLOZIN**

**Definition of Investigational Product:** A pharmaceutical form of an active substance or placebo being tested or used as a reference in a clinical study, including products already with a marketing authorization but used or assembled (formulated or packaged) in a way different from the authorized form, or used for an unauthorized indication, or when used to gain further information about the authorized form. In this protocol, the investigational product is Canagliflozin.

**Definition of Non-Investigational Product:** Other medications used in the study as support or escape medication for preventative, diagnostic, or therapeutic reasons as components of a given standard of care. In this protocol, the non-investigational products are Metformin, Insulin, GLP-1 agonists, sulfonylureas, and DPP-IV inhibitors. Patients will continue on any combination of the following anti-diabetic therapies: metformin (1-2 grams), insulin, GLP-1 agonists, a DPP-IV inhibitor, or sulfonylureas, as per their study entry dose added to Cana or placebo. As mentioned

before, patients on oral hypoglycemic other than any combination of the following anti-diabetic therapies: metformin (1-2 grams), insulin, GLP-1 agonists, a DPP-IV inhibitor, or sulfonylureas will not be invited to join the study.

This study is being conducted under FDA mandated guideline for use in type 2 diabetes. Though in this particular study Cana is referred to as the investigational drug, it is not a novel drug and we should not need a separate IND for execution of this study.

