### **Study Design Overview:**

We propose a 2-arm randomized, double-masked, placebo-controlled, parallel group, longitudinal study of 16-weeks duration. (See study design below), recruited over 2 years. The 16 week time interval has been previously shown adequate to observe changes in endothelial progenitor stem cells, biochemistry and importantly, PWV changes. Patients will be randomized to 2 groups:

Control, (n=20), metformin, insulin or Combo + Placebo

Treatment, (n=20) metformin, insulin or Combo + Cana 100mg

This proposed study is based on patients with type 2 diabetes, who are on any combination of the following anti-diabetic therapies: metformin (1-2 grams), insulin, GLP-1 agonists, a DPP-IV inhibitor, or sulfonylureas but still remain poorly controlled with HbA1C between 7.0% and 10% (both inclusive), but not overtly out of control (> 10% of HbA1C).

Though our study is over 16 weeks we do not anticipate significant drop in HbA1C in between the two groups in this relatively short time period to act as a confounding factor on CD34+ cell number, function and gene expression.

Subjects will be taking 100 mg of Cana or placebo. Dose titration of metformin, will not be allowed. Dose titration of insulin will be allowed to avoid hypoglycemia while maintaining HbA1C under 10%.

Most clinical studies looking at HbA1C reduction were of a much longer duration of 6 months or above and most DPP-4 inhibitor studies are with animal EPCs where comparison with human CD34+ population is difficult to make. In one study where saxagliptin was used for 12 weeks

in drug-naïve type 2 diabetes patients there was placebo-subtracted HbA1c reduction noted of 0.45-0.63%. It showed mean placebo-subtracted reductions in fasting serum glucose of 20 mg/dL. From our laboratory studies of in vitro human EPC studies we do not think glucose level change of 20 mg/dL is significant enough to account for changes in EPC number, function and gene expression. However we will take the possibility of glycemia change/ reduction in experimental arm into account during statistical analysis of the results between the Canagliflozin and placebo groups.

*Visits with outcome measurements* will be scheduled for the morning while overnight fasting (except water) to reduce diurnal variability, and clinical parameters will be obtained at scheduled office visits as depicted in the study schema and will be measured at each outcome visit as follows:

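### Fasting insulin and HOMA-IR do not validly measure insulin resistance in participants injecting insulin, and insulin titration after randomisation could bias the arm comparison

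*Combined protocol and SAP*

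**What the plan says.** **Outcomes.** The secondary outcomes in the Protocol Synopsis include glycaemic control, assessed by fasting glucose, "insulin, and HbA1c levels and assessing insulin resistance using HOMA-IR". Section 2 (Effect of Cana on Serum Biochemistry) repeats this: "Fasting blood glucose, insulin and lipid profile will be used to assess insulin resistance". Neither place limits the measures to a subset of participants.

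**Eligibility.** The synopsis admits patients on any combination of "metformin (1-2 grams), insulin, GLP-1 agonists, a DPP-IV inhibitor, or sulfonylureas as therapy for their Type 2 Diabetes". Section 3 (Study Population), Section 4 (Study Treatment) and Section 6 (Patient Definition and Selection) agree. No section caps the share using insulin.

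**Background dose.** The synopsis outcome statement and the Section 3 design heading describe patients on a stable dose. Section 4 says background drugs continue "as per their study entry dose added to Cana or placebo". Section 6 (Study Design Overview) rules out metformin titration but then says: "Dose titration of insulin will be allowed to avoid hypoglycemia while maintaining HbA1C under 10" percent.

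**Handling.** Section 4 describes permuted-block randomisation and names no stratification factor. Section 7 (Data Analysis) adjusts for imbalances seen by inspection and gives glucose as its example of a time-varying covariate. It names neither insulin use nor insulin dose. Outcome visits are fasting, but no section states when background insulin is taken relative to the blood draw. No insulin assay is specified and C-peptide is not listed.

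**GLP-1.** Sections 2 and 6 also list an assay: "Plasma SDF1 alpha (ELISA) and GLP-1 (ELISA) will be estimated to assess endothelial health". The same sentence adds a second purpose, namely factors that may affect CD34+ cell chemotaxis.

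**The concern.** HOMA-IR is built from fasting glucose and fasting insulin and treats the insulin as the patient's own response to that glucose. In a participant who injects insulin, the measured concentration can mix administered and endogenous insulin, so the index no longer measures resistance in that participant.

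The more serious issue is a dose change after randomisation. The stated reason for titration is to avoid hypoglycaemia, and one arm receives an added glucose-lowering drug, so cuts could be more frequent there. Masking does not prevent this, because the decision follows glucose and not knowledge of allocation. A lower injected dose can lower measured insulin, and therefore HOMA-IR, with true resistance unchanged. The trial could then report improved insulin resistance on canagliflozin that is only a change in injected insulin.

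**Working it through.** There is no figure in the plan to reproduce. The sample size rests on CD34+ cell counts, and the 73% power in the synopsis is not tied to HOMA-IR or insulin. The documents give no share of insulin users, no rate or size of dose cuts, and no SD for HOMA-IR. Everything below is illustration on assumed inputs.

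**1. Why glucose adjustment does not help.** The plan does not write out the index; the standard form is HOMA-IR = glucose × insulin ÷ constant. On the log scale, ln(HOMA-IR) = ln(glucose) + ln(insulin) − constant. The artefact sits in the insulin term. Putting glucose in the model, as Section 7 allows, leaves that term untouched.

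**2. One down-titrated user.** Let s be the share of fasting insulin that is injected (assumed 30% to 70%) and c the dose cut (assumed 10% to 30%). At unchanged glucose and unchanged resistance, the fall in HOMA-IR is s × c:
- low: 0.3 × 0.1 = 3%
- middle: 0.5 × 0.2 = 10%
- high: 0.7 × 0.3 = 21%

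**3. The arm comparison.** Let f be the share of the active arm using insulin. Assume every one of them is cut and no placebo user is. The arm difference is then about f × (s × c):

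| f | low (3%) | middle (10%) | high (21%) |
|---|---|---|---|
| 25% | 0.75% | 2.5% | 5.25% |
| 50% | 1.5% | 5% | 10.5% |

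Geometric means give nearly the same: 0.97^0.25 = 0.992 to 0.79^0.25 = 0.943 at f = 25%, and 0.97^0.5 = 0.985 to 0.79^0.5 = 0.889 at f = 50%. Fewer cuts on active, or any cuts on placebo, shrink these figures.

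**4. Chance imbalance from stable use.** The protocol hopes to retain 16 per arm. With independent binomial counts and no stratification, the chance that the arms differ by at least 20 percentage points in use of a drug class is about 15% if 25% of patients use it and about 22% if 50% do.

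**5. What restricting to non-users does to power.** Take a true standardised effect d = 0.91 in non-users (the value giving 73% power at 16 per arm, two-sided 0.05), no interpretable signal in users, and equal SD. By the normal approximation, power = Φ(d × √(n/2) − 1.96). In the all-patient analysis d is multiplied by (1 − f):
- f = 25%: all patients 49%; non-users only (12 per arm) 61%
- f = 50%: all patients 25%; non-users only (8 per arm) 44%

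Under these assumptions, dropping uninterpretable values gains more than the lost numbers cost.

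**The case against.** The strongest reply is that the trial is randomised and placebo-controlled, that Section 4 continues background drugs at entry dose, and that the analysis is a group-by-time comparison with a patient random effect. Stable insulin use is therefore balanced in expectation and largely cancels in the contrast. That stands: stable use is a matter of noise, dilution and chance imbalance. It does not make HOMA-IR valid in insulin users, and it does not cover titration after randomisation.

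The plan also expects no significant between-group fall in HbA1c over 16 weeks, and no section quantifies hypoglycaemia or titration by arm. So differential titration is possible, not shown. Similar HbA1c would not rule it out, since cutting insulin in one arm would itself narrow an HbA1c difference. How far measured insulin includes the injected product also depends on an assay that the documents do not name.

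Three stronger readings are tempting and not supported:
- A reader might infer that these measures reflect background drugs in the whole trial. The argument reaches only users of those drugs, whose share is not given; participants not on insulin can give interpretable HOMA-IR values.
- A reader might take 3% to 21% as the bias in the trial result. It is the change in one down-titrated user. The arm effect is smaller, as shown above.
- A reader might extend the bias to plasma GLP-1, because GLP-1 agonists and DPP-IV inhibitors are allowed. Section 6 permits titration of insulin and does not mention titrating those drugs, so the same route to bias between arms is absent. For the stated chemotaxis purpose, GLP-1 altered by a background drug may be relevant exposure and not contamination.

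**Conclusion.** The concern holds for fasting insulin and HOMA-IR in participants injecting insulin. As written, the plan applies both measures to everyone, allows insulin titration after randomisation, and has no restriction, stratification or named covariate to deal with it. The possible spurious arm difference in HOMA-IR is about 1% to 5% with 25% insulin users and about 1.5% to 10.5% with 50%. Those ranges rest on an assumed injected share, an assumed dose cut, unchanged glucose, every active-arm user cut and no placebo user cut. The true size cannot be derived from the documents.

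These are secondary outcomes in a self-described pilot. The treatment comparison on the CD34+ endpoints is not affected by this point, and fasting glucose and HbA1c do not share the measurement problem. The change is worth making because it is cheap and because a reported improvement in insulin resistance could not otherwise be interpreted. Plasma GLP-1 is a lesser matter of presentation.

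**What to change.** In the synopsis outcome measures, the Section 2 secondary objective and serum biochemistry text, the matching Section 6 serum biochemistry text, and Section 7 (Data Analysis):

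- State that the main analysis of fasting insulin and HOMA-IR is in participants not using insulin at baseline, and report n per arm. This subset is fixed before randomisation. Requiring no insulin through week 16 would condition on events after randomisation that may depend on arm, and should be avoided.
- Record insulin use and dose at each visit and summarise changes by arm.
- Give the all-participant result only as a sensitivity analysis, labelled as affected by injected insulin.
- Keep fasting glucose and HbA1c as the all-patient glycaemic outcomes.
- Show plasma GLP-1 also by baseline use of a GLP-1 agonist or DPP-IV inhibitor, without excluding those users.

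Separately, the synopsis and Section 3 (stable dose), Section 4 (study-entry dose) and Section 6 (insulin titration allowed) must be reconciled.

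The cost is wording plus recording insulin dose at visits already scheduled. Fewer participants contribute to two secondary measures, so their intervals may widen.

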Our preliminary data indicates that mRNA gene expression of both SGLT1 and SGLT2 are noted on human CD34+ cells however only SGLT2 mRNA gene expression is up-regulated several fold in human CD34+ cells in presence of hyperglycemia (20mM glucose). However non primary commercially obtained human endothelium (HUVEC) do not show similar results. An explanation could be SGLT2 expression decreases as the cell transitions from progenitor to mature endothelium. From these results we believe SGLT2 inhibitor will be effective on progenitors and not mature endothelium. We therefore hypothesize that CD34+ cells will be an ideal biomarker to study the effect of the drug. It is possible that Cana, by blocking SGLT2 receptors, may influence other CD34+ cell surface receptors including other glucose transporters and influence its function (most importantly migration). If a particular medication positively influences stem/progenitor cell migration then that medication can positively influence endothelial dysfunction and vascular complications from diabetes. We are particularly interested to note effect of Canagliflozin, a SGLT2 inhibitor on other glucose transporters such as GLUT 1 and 4 while looking at SGLT 1 and 2 on CD34+ cells. It will be helpful to discern these effects particularly when choice of oral diabetic medication in a type 2 diabetes population is practically limited to metformin, DPP4 inhibitors and SGLT2 inhibitors. We plan to investigate the effect of Cana on CD34+ cells, in a placebo matched study. We plan to recruit subjects with type 2 diabetes with the following characteristics: 1) overweight, mild and moderately obese (BMI=25.0-39.9); 2) individuals with type 2 diabetes with inadequate control, HbA1C= 7 to 10.0%, on any combination of the following anti-diabetic therapies: metformin (1-2 grams), insulin, GLP-1 agonists, a DPP-IV inhibitor, or sulfonylureas 3) with no current macrovascular complications. As per the ADA [2], Metformin, insulin, GLP-1 agonists, DPP-IV inhibitors, and sulfonylureas are all 1st line of care along with life-style modification. While Metformin on its own may affect inflammatory biomarkers, the effect is minimal at best, particularly in presence of endothelial dysfunction. For accurate comparison, both placebo and the Canagliflozin group will be on any combination of the following anti-diabetic therapies: metformin (1-2 grams), insulin, GLP-1 agonists, a DPP-IV inhibitor, or sulfonylureas We will recruit a total of 40 patients (20 individuals/per group) with approximately a 20% drop out rate over two years and we hope to retain 32 individuals (16/group). Individuals in each group will be matched by sex, age, and race. Participants will be assessed at baseline (week 0), and at 2 and 4 months of drug intake.

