## 7 STATISTICAL CONSIDERATIONS

### **STATISTICAL ANALYSIS**

Sandri et al. (2005, Study A, patients with peripheral arterial occlusive disease) found that in the control group, CD34+ cells increased from 372 cells per mL blood at baseline (SD 156) to 402 (SD 183) at 4 weeks. In their exercise training group, the increase was from 458 (SD 252) at baseline to 2977 (SD 852) at 4-weeks. We created a simulated data set with these parameters in order to calculate the percent of CD34+ cell variation that was explained by the group x time interaction. We tested two random effects mixed models, one without and the other with, a group x time interaction (group is treatment vs control; time is pre vs. 4-weeks post). The percent variance explained =  $(V_{no-int} - V_{int})/V_{no-int}$ , where  $V_{no-int}$  is the residual covariance parameter estimate without a group x time interaction term in the model, and  $V_{int}$  is the residual covariance parameter estimate with a group x time interaction term in the model. We found that based on the baseline and 4-week mean and standard deviation of CD34+ cell concentrations reported by Sandri et al. (2005), the interaction explained 84.5% of the variance in CD34+ cell concentration (a very large effect size). The correlation among repeated measures was  $r=.62$ . Using these parameters in G-Power3 (version 3.1.3), with 2 groups measured at 2 time points, in order to achieve power  $>.95$  would require a total sample size of 6 subjects (3 per group) each measured at 2 time points. Assuming 25% subject loss, we would need to start with 4 per group. If the group x time interaction explained only 50% of the variance in CD34+ cell count (still a large effect), we would need total sample size of 8 (4 per group) in order to achieve power  $>.95$ . In order to account for possible 25% drop-out, 6-8 per group should be randomized.

In Sen et al. (2015), in a sample of patients with pre-diabetes ( $n=11$ ), CD34+ cell number increased from 0.8 (SEM 0.1) before exercise, to 1.4 (SEM 0.2) after exercise, a pre-post effect size (Cohen's  $d$ ) of 1.81. In order to detect an effect of this size using a 2-tailed paired t-test, with  $\alpha=.05$ , for power  $>.80$ ,  $>.90$ , and  $>.95$ , the number of subjects required would be 5, 6, or 7, respectively.

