However the two quoted studies quoted above are very different from our proposed study on patients' with established endothelial dysfunction entity such as diabetes. It is well known (Werner et al, Ref No. 11) that diabetes can affect CD34+ number and function, therefore in our proposed study, number of CD34+ cell availability may be a limiting factor. Therefore we propose to use double the number suggested by power calculation and use  $8 \times 2 = 16$  patients per group so that CD34+ cell based end-point studies are not compromised.

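### The synopsis reports 73% power and points to the statistics section, but Section 7 contains no such figure and its stated effects do not produce it

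*Combined protocol and SAP*

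**What the plan says.** The Statistics row of the Protocol Synopsis asks for 20 patients per group after attrition. It says "This is a pilot study; as a result appropriate power calculation is not feasible", and then "We however did conduct power analysis, which provided us with 73% power (see statistics section"). On the basis for sizing it says "Sample size estimates were based on the effects of exercise on CD34+/KDR+ cells as described in the literature".

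Section 7 (Statistical Analysis) reports required sizes only:

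- From a two-group exercise study in peripheral arterial disease, the group-by-time interaction explains 84.5% of the variance in CD34+ cells (repeated-measures correlation .62), and 6 patients in total give power above .95. If it explains 50%, 8 in total are needed. On attrition: "In order to account for possible 25% drop-out, 6-8 per group should be randomized".
- From a prediabetes exercise study with n = 11, "cell number increased from 0.8 (SEM 0.1) before exercise, to 1.4 (SEM 0.2) after exercise", reported as d = 1.81. "In order to detect an effect of this size using a 2-tailed paired t-test", 5, 6 or 7 subjects are said to give power above .80, .90 and .95.

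The section then says "However the two quoted studies quoted above are very different from our proposed study" and doubles 8 to 16 per group because CD34+ cells may be scarce. It attaches no power to 16 and does not mention 20 per group. The Introduction expects "approximately a 20% drop out rate over two years and we hope to retain 32 individuals (16/group").

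**The concern.** A cross-referenced power figure should be found, or be reproducible, at the place cited. This one is the only power stated for the trial at its actual size. It also follows directly on a statement that no appropriate calculation is possible, so the two sentences pull against each other. Someone reading only the synopsis would take 73% as the chance of detecting a plausible effect, but could not say what effect, on what scale or by what test. Section 7 answers a different question: how few patients would detect very large exercise effects from studies it then describes as unlike this one.

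The prediabetes calculation has a related gap. A paired t-test needs the mean change divided by the SD of the change. The section gives neither that SD nor the pre-post correlation from which it could be derived.

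**Working it through.** **Inputs.** From the synopsis: alpha .05 and 20 per arm. From the Introduction: 16 completers per arm after 20% loss. From Section 7: 84.5% and 50% of variance explained; d = 1.81; n = 11; means 0.8 and 1.4 with SEMs 0.1 and 0.2. All tests are two-sided.

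**1. What can be reproduced.** Randomised number: 16/(1 − 0.20) = 20 per arm, as stated. Paired sizes: entering 1.81 as the paired effect gives power .851, .938 and .976 at n = 5, 6 and 7, so 5/6/7 follows if 1.81 is the paired effect.

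**2. Power at 16 per arm from Section 7's own effects.**

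- Variance explained: f² = p/(1 − p), which is 5.45 for 84.5% and 1.00 for 50%. With noncentrality f² × N, N = 32 and df 1 and 30, power is 1.000 and .9998. This form leaves out the correlation of .62; including it raises power further.
- d = 1.81 taken as a two-sample effect: noncentrality 1.81 × √(16/2) = 5.12 on 30 df gives .9986. At 20 per arm it gives .9998.

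None of these is near 73%.

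**3. What 73% would require.** Solving the noncentral-t power of a two-sample test for the difference gives 0.940 SD at 16 per arm and 0.835 SD at 20. Neither appears in the documents.

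**4. The paired effect size.** SD = SEM × √11, so the SDs are 0.332 before and 0.663 after. The mean change is 0.6, and 0.6/0.332 = 1.81, which matches the stated d. The SD of the change is √(0.332² + 0.663² − 2r × 0.332 × 0.663) = √(0.55 − 0.44r). Section 7 gives no r for this study, so r is varied as an assumption:

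| Assumed r | SD of change | Paired effect | n for >.80 / >.90 / >.95 |
|---|---|---|---|
| 0 | 0.742 | 0.81 | 15 / 19 / 22 |
| .5 | 0.574 | 1.04 | 10 / 12 / 14 |
| .9 | 0.392 | 1.53 | 6 / 7 / 8 |
| 1.00 | 0.332 | 1.81 | 5 / 6 / 7 |

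With the SEMs exactly as printed, a paired effect of 1.81 needs a correlation of 1.00. The means and SEMs are rounded to one decimal, however. If the post SEM were 0.15, a paired effect of 1.81 arises at r = .75. If the change were 0.7 with SEMs of 0.095 and 0.15, it arises at r of about 0.63.

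**5. What the planned size can detect.** With complete data at weeks 0, 8 and 16 and time entered linearly, week 8 has zero weight in the slope. The group-by-time contrast is then the difference in week 16 minus week 0 change, and a two-sample t-test on that change approximates it. At 16 per arm:

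| Difference (SD of change) | Power |
|---|---|
| 1.02 | .797 |
| 0.8 | .591 |
| 0.5 | .278 |

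**The case against.** The strongest reply is that this is a declared pilot. The 16 per group comes from doubling 8 on grounds of cell availability, not from a power target, so a stray percentage changes nothing. That is right about the consequences, but the protocol chose to report a figure and to say where it comes from, and it is not there.

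A second reply is that an unshown calculation may lie behind it. Some combinations land within a point: a normal approximation with d = 0.905 (0.6/0.663) at 16 per arm gives 72.6%, and with d = 0.809 (0.6/0.742) at 20 per arm 72.5%; a one-sided exact test with d = 0.809 at 16 per arm gives 72.3%. Section 7 states none of these effects, so they do not source the figure. They are a reason to let the sponsor supply the calculation instead of insisting on deletion.

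A reader might infer that dividing by the baseline SD is a proven error in the paired t-test. The documents do not support that. Section 7 names no denominator, and rounding leaves room for 1.81 to be a genuine paired effect. A reader might also take 25% and 20% loss as contradictory assumptions for this trial. The 25% pads the illustrative sizes that Section 7 then sets aside; the trial's own rate is 20%, and it reproduces 20 per arm.

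Finally, the change-score powers ignore partial data from dropouts and the covariate and glucose adjustment described under Data Analysis. That limitation stands, so they are approximate. Figures for time as a class variable are best left out: they depend on variance components, including the random effect for time, that the plan does not specify.

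**Conclusion.** The 73% is unsupported. It appears only in the synopsis, the section it cites does not contain it, and that section's effects give .998 or more at 16 per arm. This rests on two-sided testing at .05 and on the effects as stated in Section 7.

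The paired sizes of 5, 6 and 7 cannot be verified from the figures shown. At face value they need a correlation of 1.00; with rounding, about 0.63 or higher could suffice; at r = .5 with the printed SEMs they would be 10, 12 and 14. This weakens a supporting argument only, because 16 per group comes from the other calculation.

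The cell population is a small wording mismatch: CD34+/KDR+ in the synopsis, CD34+ in the Section 7 sizing.

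Nothing here shows that 40 patients is the wrong number for a pilot or that the planned analysis is invalid. The fault is in what the synopsis tells the reader, and it is worth correcting.

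**What to change.** Delete the 73% from the synopsis, or add to Section 7 the calculation that produced it: effect, SD, test and number per arm. If it is deleted, keep the pilot statement and add:

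> With 16 completers per arm (20% loss) and two-sided 0.05, a two-sample t-test on change from week 0 to week 16 has about 80% power at 1.02 SD of the change score, 59% at 0.8 SD and 28% at 0.5 SD.

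In Section 7, state the denominator of 1.81 and the pre-post correlation from the source data. If 1.81 is not the paired effect, recompute or remove 5, 6 and 7. Use one cell-marker name in the synopsis and Section 7.

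The cost is wording in two places, plus a look at the prediabetes study's data. There are no extra patients, visits or analyses. The one downside is that the stated power will look less favourable.
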